5.1.3 Exploratory Endpoints

CCI

5.2 CCI CCI STUDY SUBJECTS

5.2.1 Definitions of Analysis Sets

The **Safety Analysis Set (SAS)** is the group of subjects who received at least one dose of study drug and had at least one post-dose safety assessment.

The **Full Analysis Set (FAS)** is the group of randomized subjects who received at least one dose of study drug and had at least one post-dose seizure measurement.

The **Per Protocol Analysis Set (PP)** is the group of subjects who sufficiently complied with the protocol. Details of the evaluability criteria are given in Section 5.2.3.

The **Pharmacokinetic Analysis Set** is the group of subjects who received perampanel and had at least one quantifiable perampanel concentration during the Maintenance Period of the Core Study and adequately documented dosing history.

The **PK/PD analysis** set is the group of subjects who received perampanel or placebo who had seizure frequency data with documented dosing history. Subjects who received perampanel should have at least one quantifiable perampanel concentration as per the PK analysis set.

The **Intention to Treat Analysis Set (ITT)** is the group of randomized subjects who received at least one dose of study drug.

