9 INVESTIGATIONAL PLAN

9.1 OVERALL STUDY DESIGN AND PLAN

This will be a multicenter, double-blind, randomized, placebo-controlled, parallel-group study of perampanel as adjunctive therapy in subjects with inadequately controlled seizures associated with LGS. The study will consist of 3 phases: Prerandomization, Randomization, and Extension. The Core Study will consist of the Prerandomization and Randomization Phases.

The Prerandomization Phase will consist of a 4- to 8-week Screening/Baseline Period during which subjects will be assessed for overall eligibility to participate in the study, including seizure activity. Baseline seizure count will be assessed using all diary data before randomization (at least 4 weeks prospectively). Following successful completion of this period, subjects will be randomized to receive perampanel or placebo in a 1:1 ratio.

The Randomization Phase will consist of 3 periods: Titration (6 weeks), Maintenance (12 weeks), and Follow-up (4 weeks, only for subjects not entering into Extension A). As required by some regulatory agencies, the following estimates are provided:

- The study will begin approximately Jan 2017 and will end approximately Jan 2020. (revised per Amendment 01)
- The maximum estimated period for each subject (except subjects continuing in Extension B) on the study is anticipated to be approximately 82 weeks. (revised per Amendment 04)

An overview of the study design is presented in [Figure 1](#).

[figure not shown]

Figure 1 Study Diagram for Study E2007-G000-338 (revised per Amendment 04)

R = randomization.

a: Subjects who do not continue in Extension A or those who prematurely discontinue from the study will return to the study site for Follow-up visits 1 week and 4 weeks after the last study drug administration.

b: Subjects will be up-titrated to optimize efficacy while maintaining good tolerability, up to a maximum dose of 8 mg/day. Once titrated, all subjects will be kept at a stable dose for at least 2 weeks (to reach steady-state) before the start of the Maintenance Period. The dose of study drug during the Maintenance Period will be the last dose achieved at the end of the Titration Period.

c: After the double-blind Conversion Period of Extension A, subjects can be titrated (except in Japan, where the maximum allowed dose remains at 8 mg/day) up to 12 mg/day in 2-week intervals, as per the investigator's discretion.

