9.1.2.2 Core Maintenance Period

During the 12-week Maintenance Period, subjects will continue treatment with the dose and formulation of test drug (perampanel) or placebo achieved during the Titration Period, taking the study drug once daily in blinded fashion. The Maintenance Period will begin with Visit 5, and subjects will continue treatment at the last dose (or matching placebo) achieved in the Titration Period. Study drug administration in the evening immediately before (and the evening on the day of) Visit 5 and Visit 6 should be withheld (all other AEDs should be administered per the subject's usual AED regimen). Study drug will be given during Visit 5 and Visit 6 at the study site (within 1 to 5 hours after dose administration). Bedtime dosing will resume in the evening on the day of Visit 5 and Visit 6. In these cases, dosing date and time of the previous 3 doses before each PK sampling visit will continued to be recorded. Parents or caregivers will complete seizure diaries throughout the Core Study; all seizure types will be collected. Subjects will continue to take their baseline anti-epileptic medications throughout the study. (revised per Amendment 04)

Dose adjustment during the Maintenance Period is not recommended; however, the investigator may down-titrate a subject's dose if, in his/her clinical judgment, the subject experiencing intolerable AE(s) that warrant(s) such an action. In general, more than one down-titration of a subject's dose will be discouraged; however, if the subject continues to present significant intolerable AE(s) and the investigator deems it is necessary, the dose may be reduced further. During the Maintenance Period, subjects whose dose has been down-titrated can have their dose increased again, as soon as tolerability improves. This can be done at an unscheduled clinic visit or at the next clinic visit after the investigator has deemed it appropriate based on the resolution of AE(s).

Subjects who complete the Maintenance Period will have the option to roll over into Extension A and will immediately begin the blinded Conversion Period.

Subjects who do not continue in Extension A or those who prematurely discontinue from the study will return to the study site for Follow-up visits 1 week and 4 weeks after the last study drug administration. (revised per Amendment 04)

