- r: Two blood samples (1.0 mL each) will be collected at Visit 5 and Visit 6 for the determination of perampanel plasma concentrations. One blood sample will be collected before dose administration and the second sample will be collected anytime between 1 to 5 hours postdose. Study drug administration in the evening immediately before (and the evening on the day of) Visit 5 and Visit 6 should be withheld (all other AEDs should be administered per the subject's usual AED regimen). Study drug will be given during Visit 5 and Visit 6 at the study site, after collection of predose PK sample (within 1 to 5 hours after dose administration). Bedtime dosing will resume in the evening on the day of Visit 5 and Visit 6. Each PK sample is to be split into 2 aliquots before storage per instructions provided in the laboratory manual. (revised per Amendment 04)
- s: One blood sample (1.0 mL) will be collected for the determination of perampanel plasma concentrations. The blood sample may be collected at any time during the specified visits
- t: A sample will be collected predose on Day 1, or at another visit if it cannot be collected at this time.

The volume of blood to be taken at each visit in the core study is shown in Table 6. The total volume of blood taken during the core study for subjects who complete all core study visits and enter Extension A will be 36 mL. For subjects who do not enter Extension A after completing all core study visits, the total volume of blood taken during the core study will be 43 mL (not including unscheduled visits). (revised per Amendments 01 and 04)

Table 6 Blood Volumes Taken During Core Study
 (revised per Amendments 01 and 04)

| Visit No. | V1 | V2 | V4 | V 5 | V 6 | V7 | EDC | Follow-up, Wk19 | Follow-up, Wk 22 | Unscheduled Visit |
|-----------------|----|----|----|-----|-----|----|-----|-----------------|------------------|-------------------|
| Chemistry | X | X | X | | | X | X | | X | X |
| Serology | X | | | | | | | | | X |
| PK sample | | | | X | X | X | X | X | | |
| Haematology | X | X | X | | | X | X | | X | X |
| PGx | | X | | | | | | | | |
| Total Vol. (mL) | 10 | 9 | 6 | 2 | 2 | 7 | - | 1 | 6 | - |

EDC = early discontinuation, V = visit, Wk = week

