9.7.1.2 Definitions of Analysis Sets

The Safety Analysis Set is the group of subjects who received at least one dose of study drug and had at least one post-dose safety assessment.

The FAS is the group of randomized subjects who received at least one dose of study drug and had at least one postdose seizure measurement.

The Per Protocol (PP) Analysis Set is the group of subjects who sufficiently complied with the protocol. Details of the evaluability criteria will be determined before database lock and treatment unblinding and will be specified in the SAP.

The Pharmacokinetic Analysis Set is the group of subjects who received perampanel and had at least one quantifiable perampanel concentration during the Maintenance Period of the Core Study and adequately documented dosing history.

The PK/PD analysis set is the group of subjects who received perampanel or placebo who had seizure frequency data with documented dosing history. Subjects who received perampanel should have at least one quantifiable perampanel concentration as per the PK analysis set.

Intention to Treat (ITT) analysis set is the group of randomized subjects who received at least one dose of study drug.

All subjects who withdraw from treatment will be summarized and their withdrawal reasons will be tabulated. Prior and concomitant medication usage and demographics will also be summarized.

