9.7.1.7 Pharmacokinetic, Pharmacodynamic, and Pharmacogenomic/Pharmacogenetic Analyses

PHARMACOKINETIC ANALYSES

Perampanel concentrations will be listed by subject, dose, and visit.

Analysis variable(s): Plasma concentrations of perampanel

Analysis methods: A population PK approach will utilize PK sample data collected during the Maintenance Phase of this study, and will be used to characterize the PK of perampanel. The effect of intrinsic (ie, demographics) and extrinsic factors (ie, most common concomitant AEDs) on perampanel PK will be evaluated. Derived exposure parameters such as area under the concentration-time curve at steady-state (AUC_{ss}) or the average steady-state drug concentration ($C_{av,ss}$) will be calculated from the model using the individual posterior estimates of CL/F and dosing history. (revised per Amendment 04)

PHARMACODYNAMIC ANALYSES

Efficacy and selected safety endpoints may be correlated against exposure and/or dose.

PHARMACOKINETIC/PHARMACODYNAMIC ANALYSES

The relationship between exposure to perampanel and response will be modeled using population PK/PD analysis.

PHARMACOGENOMIC ANALYSES

Pharmacogenomics analyses may be performed and reported separately. Details of these analyses may be described in a separate analysis plan.

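### The PK/PD set excludes perampanel subjects who leave during Titration but keeps placebo subjects who do, although a PK sample is scheduled when they leave

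*SAP*

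**What the plan says.** Protocol 9.7.1.2, the protocol synopsis (Analysis Sets) and Core Study SAP 5.2.1 give the same rules.

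- **PK set.** Perampanel subjects who "had at least one quantifiable perampanel concentration during the Maintenance Period of the Core Study and adequately documented dosing history".
- **PK/PD set, both arms.** In the SAP, the PK/PD analysis "set is the group of subjects who received perampanel or placebo who had seizure frequency data with documented dosing history". No study period is named.
- **PK/PD set, perampanel only.** "Subjects who received perampanel should have at least one quantifiable perampanel concentration as per the PK analysis set".

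On timing, protocol 9.1 states: "The Randomization Phase will consist of 3 periods: Titration (6 weeks), Maintenance (12 weeks), and Follow-up". Protocol 9.1.2.2 adds: "The Maintenance Period will begin with Visit 5".

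On sampling, footnote r of Table 5 (protocol 9.5.2) says: "Two blood samples (1.0 mL each) will be collected at Visit 5 and Visit 6 for the determination of perampanel plasma concentrations". Footnote s covers one further sample at Visit 7, at Early DC and at the 1-week Follow-up visit: "The blood sample may be collected at any time during the specified visits". SAP 5.5 also lists a sample at early termination. No PK sample is scheduled at Visits 2 to 4.

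On use of the data, protocol 9.7.1.7 says: "A population PK approach will utilize PK sample data collected during the Maintenance Phase of this study". Exposure is then derived from each subject's posterior clearance estimate and dosing history. SAP 5.5 leaves the modelling methods to a separate analysis plan.

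**The concern.** The two arms enter the PK/PD set under different rules, and the difference depends on something that happens after randomization. Dose rises from 2 to 8 mg/day over the Titration Period (protocol Table 1), and protocol 9.1.2.1 names intolerance as a reason for discontinuing then. Being in the perampanel part of the set is therefore plausibly related to tolerability, while being in the placebo part is not. Randomization no longer protects the comparison of exposed subjects with placebo.

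Missing data do not force the exclusion. A Titration leaver who attends the Early DC visit is sampled, but that concentration does not count because it was not drawn in Maintenance.

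The rule also departs from the efficacy plan. The primary endpoint spans Titration and Maintenance. The responder rule in SAP 5.4.2 uses whatever double-blind data an early discontinuer has. Titration leavers thus count in both arms of the FAS but in only one arm of the PK/PD set. What is at stake is secondary objective 8, the PK/PD relationships.

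**Working it through.** The documents give no size, power or dropout figure for the PK/PD set, so there is no stated figure to reproduce.

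**1. Timing.** Titration lasts 6 weeks, so Maintenance starts on Day 6 × 7 + 1 = 43. This agrees with Visit 5 in Table 5 (Week 7, Day 43), which is also the first scheduled PK visit.

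**2. Two subjects who leave on Day 30.** Both have diary data and a documented dosing history.

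| Condition | Perampanel | Placebo |
|---|---|---|
| Seizure data and dosing history | met | met |
| PK sample scheduled at Early DC | yes | yes, but only active-arm samples are analyzed (9.5.1.4) |
| Quantifiable concentration in Maintenance | required, not met | not required |
| In the PK/PD set | no | yes |

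**3. Set size.** Inputs are 71 subjects per arm (protocol 9.7.2) and an assumed share w of the perampanel arm leaving in Titration. The number able to enter is 71 × (1 − w):

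- w = 5%: 71 × 0.95 = 67.5
- w = 10%: 71 × 0.90 = 63.9
- w = 15%: 71 × 0.85 = 60.4

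The placebo arm can contribute up to 71 whatever its own dropout.

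**4. Effect on an arm-level responder rate.** The sample size section assumes 20% on placebo and a 30-point difference for drop seizures, so 50% on perampanel. Let q be the response rate among leavers, which is also an assumption. The rate among those kept is (0.50 − w × q) / (1 − w).

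| w | q = 0% | q = 20% | q = 50% |
|---|---|---|---|
| 5% | 0.500/0.95 = 52.6% | 0.490/0.95 = 51.6% | 0.475/0.95 = 50.0% |
| 10% | 0.500/0.90 = 55.6% | 0.480/0.90 = 53.3% | 0.450/0.90 = 50.0% |
| 15% | 0.500/0.85 = 58.8% | 0.470/0.85 = 55.3% | 0.425/0.85 = 50.0% |

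The shift is 0 to about 9 points if leavers respond no better than stayers. If they responded better, the kept rate would fall below 50%. This is an arm-level rate, not an exposure-response slope.

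**5. An exception.** Protocol 9.3.3 lets a subject stop drug and stay in the study. Appendix 2 gives a half-life of about 25 to 105 hours. Seven days (168 hours) after stopping, the remaining share is 0.5^(168/25) = 1% to 0.5^(168/105) = 33%. Someone who stopped a week before Visit 5 could still have a quantifiable Visit 5 sample and qualify.

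**The case against.** **The modelling plan is separate and the verb is *should*.** The separate plan could relax the rule. That stands as a possibility, but SAP 5.5 defers the modelling methods only. The sets are defined in SAP 5.2.1 and protocol 9.7.1.2, and neither document plans a check on Titration leavers.

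**Maintenance sampling has a rationale.** Subjects are to be at a stable dose for at least 2 weeks beforehand, and endpoint 9 is Cav,ss in Maintenance. This supports the restriction for endpoint 9. It does not support it for every use: protocol 9.4.4 reports clearance independent of dose and time in the paediatric analysis, so a Titration concentration with a dosing record can inform clearance.

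**Nothing confirmatory depends on the set.** This is correct. The synopsis even describes graphical exploration first, with modelling only of a relationship that emerges.

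A reader might also infer three stronger claims that the documents do not support:

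- *The rule inflates the efficacy relationship and hides the safety one.* The direction is not shown. Early leavers may have low exposure because dose is still rising, so removing them could move either slope up or down.
- *Adverse events that end treatment in Titration vanish from all exposure-related safety work.* SAP 5.6 runs safety on the Safety Analysis Set, with TEAEs by dose at onset, exposure-adjusted rates and TEAEs leading to discontinuation. Protocol 9.7.1.7 also allows correlation with dose, which needs no sample.
- *Only subjects who tolerated drug to Week 7 remain.* The condition is a quantifiable Maintenance sample. Down-titrated subjects remain, and step 5 of the working shows that some who stopped late could too.

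**Conclusion.** The concern holds as a difference in entry rules between the arms. A perampanel subject who leaves the study in Titration is outside the PK/PD set and a matching placebo subject is inside it, although a sample that could qualify the former is already scheduled. Exposure-response against placebo is therefore estimated on a one-sided, post-randomization selection plausibly linked to tolerability.

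Neither the size nor the direction of any resulting bias can be computed. The 5-15% loss is an assumption. The upper figures of 53-59% also require that no leaver responds, although SAP 5.4.2 would score leavers on their available data and could count some as responders.

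The consequence is confined to secondary objective 8. The primary and key secondary tests use the FAS, and the safety summaries use the Safety Analysis Set. It is worth correcting because the correction is cheap, not because a main result is threatened.

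**What to change.** 1. Define the PK set, and through it the PK/PD set, so that a perampanel subject qualifies with one or more quantifiable plasma levels from any visit in double-blind treatment, the Early DC visit included, together with adequate dosing records.
2. Let the population PK analysis use those samples as well as the Maintenance samples.
3. Keep the Maintenance restriction for Cav,ss (endpoint 9) only.
4. Report exposure-response with and without Titration leavers, omitting them from both arms in the second run so that the rule is the same.
5. In the main analysis, do not give model-predicted exposure to perampanel subjects who have no quantifiable sample. Some of them may not have taken the drug, and a prediction from recorded dosing would assign them exposure. At most, include them in a sensitivity analysis.

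The same wording is needed in the protocol synopsis (analysis sets and pharmacokinetic analyses), protocol 9.7.1.2 and 9.7.1.7, SAP 5.2.1 and the separate PK/PD analysis plan.

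**Cost.** Wording changes only, with no new samples. A few subjects would contribute less precise exposure estimates from a single sample that may precede steady state. Some asymmetry remains: perampanel subjects with no quantifiable sample, including leavers who miss the Early DC visit, stay outside the main set, and their number should be reported.

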5.2.2 Subject Disposition

The number of subjects enrolled and the reasons for screen failure will be summarized.

Subject disposition tables will include the number (percentage) of subjects who were:

- Randomized into each treatment group;
- Completed the study;
- Discontinued early from the study, summarized by primary reason for discontinuation.

Subject disposition will be summarized overall and by age group.

5.2.3 Protocol Deviations

The following provide definitions of major protocol deviations; however, exclusions from the PP Analysis Set will be made on a case-by-case basis using these as a guideline and based on reasonable clinical judgment.

- Subject did not meet Inclusion Criterion #4, which was: Subjects must have experienced at least 2 drop seizures per week in the 4-week Baseline Period preceding randomization.

- At any time during the study, subject stopped or interrupted any approved antiepileptic drugs (AED)s he/she was taking upon study entry.
- Subject received incorrect study drug longer than he/she received randomly assigned study drug.
- Subject had <80% study medication compliance
- Subject had <80% diary compliance during the Prerandomization and Randomization Phases.

Other criteria may be identified during the course of the study. Identification of subjects with major protocol deviations will occur before DBL and treatment unblinding.

5.2.4 Demographic and Other Baseline Characteristics

Demographic and other baseline characteristics for the SAS will be summarized for each treatment group using descriptive statistics. Continuous demographic and baseline variables include age, weight, height and body mass index (BMI); categorical variables include sex, age group (2-<12, 12-<18, 18-<65, ≥65), race and ethnicity.

MEDICAL HISTORY

The number (percentage) of subjects reporting a history of any medical condition, as recorded on the case report form (CRF), will be summarized for the SAS for each treatment group and overall. A subject data listing of medical and surgical history will be provided.

Epilepsy-specific medical history for the SAS will be summarized for each treatment group and by age group using descriptive statistics, including time since diagnosis and seizure type.

5.2.5 Prior and Concomitant Therapy

All investigator terms for medications recorded in the CRF will be coded to an 11-digit code using the World Health Organization Drug Dictionary (WHO DD) (Mar 2021). The number (percentage) of subjects who took prior and concomitant medications will be summarized on the SAS by treatment group, Anatomical Therapeutic Chemical (ATC) class (i.e., anatomical class, therapeutic class, pharmacologic class) and WHO DD preferred term. Prior medications are defined as medications that stopped before the first dose of study drug. Concomitant medications are defined as medications that (1) started before the first dose of study drug and were continuing at the time of the first dose of study drug, or (2) started on or after the date of the first dose of study drug up to 14 days after the subject's last dose. All medications will be presented in subject data listings.

The number of baseline AEDs will be summarized by treatment group and by age group and a summary of baseline and concomitant AEDs will be produced by treatment group and by age group. A baseline AED is an AED taken at the date of randomization. Concomitant AEDs are defined as above for concomitant medications.

5.2.6 Treatment Compliance

For subjects taking tablets, percent compliance will be calculated for the Randomization Phase and by visit for the FAS as follows:

$$\text{Compliance} = \frac{\text{Total number of tablets dispensed} - \text{Total number of tablets returned} \times 100}{\text{Planned total number of tablets to be taken}}$$

For subjects taking oral suspension, percent compliance will be calculated for the randomization phase and by visit for the FAS as follows:

$$\text{Compliance} = \frac{\text{Total weight in grams dispensed} - \text{Total weight in grams returned} \times 100}{\text{Planned total volume in mL to be taken} \times \text{suspension density of 1.07 grams per mL}}$$

Where subjects have taken both tablets and oral suspension, overall compliance will be derived by averaging the visit compliance across the Randomization Phase.

Overall compliance with study medication will be summarized using descriptive statistics for each treatment group and by age group. Subjects will also be categorized by compliance categories of <80%, 80%-120% and >120%.

